#### PK/PD modelling

Population PK and PK/PD models may be developed to address objectives that require an integrative interpretation of the study results. These include assessment of the dose proportionality, investigation of the nature of the PK/PD relationship, and the use of study results as part of a larger model-based data analysis. If population PK/PD models are developed, a separate Pharmacometrics Analysis Plan will be written.

### Exploratory analyses

Exploratory data-driven analyses can be performed with the caveat that any statistical inference will not have any confirmatory value.

Deviations from the original statistical plan will be documented in the clinical study report.

# 2.13.7 Interim analysis

No interim analysis is planned.

## 2.13.8 (Statistical) criteria for termination of the trial

Not appliable for this study.

## 2.13.9 Procedure for accounting for missing, unused and spurious data

All missing or incomplete safety and PD data, including dates and times, are treated as such. Missing test results or assessments will not be imputed. Missing PD data, indicated as 'M' in the data listing, will be estimated within the statistical mixed model using SAS PROC MIXED.

For graphical and summary purposes PD and safety values below the limit of quantification will be set to half (½) of the limit of quantification. For analysis no undetermined values will be replaced. For graphical and summary purposes of drug concentrations, values below the limit of quantification (BLQ) will be set to zero.

For calculation of PK parameters, all BLQ plasma concentrations occurring prior to  $C_{\text{max}}$  will be replaced by 0, except for embedded BLQ values (between two measurable time points) which will be treated as "missing". All BLQ values after  $C_{\text{max}}$  will be treated as "missing". If data points for plasma concentrations are missing, the AUC parameters will be derived by interpolating with regard to the two neighbouring non-missing concentrations. If the actual sampling time is missing, but a valid concentration value is measured, the scheduled protocol time will be used for the calculation of PK parameters.

The handling of missing, unused and spurious data will be documented in the study report.

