- Follow up (FU) visit after last treatment.
- Only weight will be measured at FU or upon early termination
- Physical examination at screening includes assessment of the Fitzpatrick skin type and evaluation of acne, freckles, tattoos or scarring on the back.
- A symptoms based physical examination will be performed.
- For women of childbearing potential: Urine beta HCG will be performed either during screening, on the first day of each treatment period or the day before the first day of each
- Treatment Period at discretion of Investigator. In either case, the results must be negative prior to dosing study participants.

  Vital signs will be measured in supine position. Oxygen saturation will be monitored after dosing at 2h until the end of study day 1 of each treatment period.
- Lunch at 0.5h and dinner 8h post dose, snack at 4.5h, time points are indicative. Light breakfast on Day 1 is shortly after wake activity around -3.5hours, after breakfast the subject starts fasting until after dosing. No meal restrictions on day -1 and day 2.
- PK sample taken 3 minutes after dosing
- Capsaicin application at screening must be performed on or before Day -5 to ensure sufficient washout between the capsaicin that is applied at screening and applied on Day 1.
- Capsaicin application will only be performed after enrolment in subjects not allergic or intolerable to the capsaicin solution, as determined at screening
- Sequence of assessments is NeuroCart® before PainCart®, for specific order of assessments see section 6.4.

  Capsaicin heat pain test (and heat pain test on control skin on volar forearm) will only be performed on subjects not allergic or intolerable to the capsaicin solution. Capsaicin heat pain task only applicable for Day 1.

  PainCart® training up to 42 days before dosing and NeuroCart® training up to 21 days before dosing.
- PainCart® and NeuroCart® will be done twice for baseline measurement
- NeuroCart® round with pEEG measurement only in second baseline measurement
- VVLT at 2u post dose will be measured is the immediate recall. VVLT at 5u post dose will be the delayed recall and recognition.
- Discharge time is approximate and only when deemed safe.

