	
 
General somatic symptoms
 
				
	
 
Cognitive symptoms
 
				
	
 
Interpersonal sensitivity
 
				
	
 
Depressed mood
 
				
	o Anxiety				
	

Hostility

				
	

Phobic anxiety

				
	

Paranoid thoughts

				
	

Psychoticism

				
	

Global severity index

				
To evaluate the blood pharmacokinetic parameters of morphine, fluvoxamine and the two drugs as combination	PK parameters of morphine (and metabolite morphine-6-glucuronide), fluvoxamine by noncompartmental analysis of the plasma concentration-time data: AUCinf, AUClast, CL(/F), Cmax, t1/2, tlag, tmax, Vz(/F)				
To evaluate the safety and	Treatment-emergent (serious) adverse events				
tolerability of morphine,	((S)AEs) throughout the study at every study visit				
fluvoxamine and the two drugs as combination	Concomitant medication throughout the study at every study visit				

Baseline for PD measurements is defined as the **average** value prior to dosing in the morning of Day 1 for each treatment period.

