#### Morphine

Morphine and M6G notably contribute to the analgesic effect after administration of morphine, which is rapidly metabolized in the liver.26 As the study aims to have a better understanding of the analgesic effects of morphine and M6G in patients with chronic neuropathic pains and generate data that may be used for PK-PD modelling, an IV dose is deemed preferable over an oral dose.

Both morphine HCl 3 mg and 7 mg will be administered as intravenous bolus injection in 1 minute. In both the treatment arm with nortriptyline + morphine, and treatment arm with placebo + morphine, the bolus injections will be administered at t = 2 h (3 mg) and t = 5 h (7 mg).

The 3 mg and 7 mg doses of morphine are equianalgesic to minimally therapeutic and clearly therapeutic doses of buprenorphine as observed in a previous study where potentiation of buprenorphine and milnacipran was assessed.  Buprenorphine is 30-40 times more potent than IV morphine.  Testing two morphine doses, one minimally therapeutic and one clearly therapeutic, on a single study day will allow for detailed exploration of possible synergistic/potentiating effects of the combination treatment during the PKPD analysis. Furthermore, the 3 mg and 7 mg morphine doses are based on a calculation using pre-existing and published morphine and pregabalin  PK/PD models. Refer to Figure 1 for the predictions of effect of these doses on PTT for the cold pressor test. As illustrated in Figure 1, the proposed doses are predicted to yield an increased analgesic effect, while expected to have manageable side effects.

**Figure 1.** Predicted effect on cold pressor PTT based on the integrated PKPD model of morphine and pregabalin. Black line is the predicted placebo response, red line the proposed morphine dose of 3mg IV at t = 2 h and 7mg IV at t = 5 h, the green line the single oral dose of pregabalin 300mg at t = 0 and blue line the combination treatment of above-mentioned doses and drugs.

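### The missing-concentration rule for AUC has no exception for a dose between the two neighbours, so one lost morphine sample makes that subject-period's AUC and CL non-comparable with the other period

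*Protocol*

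**What the plan says.** Section 2.13.9 sets the concentration-handling rules for PK parameters. BLQ values before Cmax "will be replaced by 0, except for embedded BLQ values (between two measurable time points) which will be treated as" missing. BLQ values after Cmax are also missing. For missing points it then says "If data points for plasma concentrations are missing, the AUC parameters will be derived by interpolating with regard to the two neighbouring non-missing concentrations". The rule covers all analytes and all routes alike.

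Section 2.7.1 (Morphine) describes the input: "Both morphine HCl 3 mg and 7 mg will be administered as intravenous bolus injection in 1 minute". The 3 mg bolus is at 2 h and the 7 mg bolus at 5 h, in both treatments.

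Table 1, read by column position, has PK samples at pre-dose, 1, 2, 4, 5, 6, 8 and 24 h. The footnote to the 2 h and 5 h samples reads "PK sample taken 3 minutes after dosing". The samples around the boluses are therefore at 1 h, 2 h 03, 4 h, 5 h 03 and 6 h.

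Table 2 (section 2.4) lists AUCinf, AUClast and CL among the secondary PK parameters. Section 2.13.6 summarises PK parameters descriptively by treatment and refers the non-compartmental procedure to an SOP that is not shown.

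**The concern.** Interpolating between neighbours is reasonable when concentration moves continuously between them, as after one oral dose. An IV bolus breaks that continuity, and here it happens twice per period. Three samples have neighbours on opposite sides of a bolus:

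- 2 h 03 (neighbours 1 h and 4 h)
- 4 h (neighbours 2 h 03 and 5 h 03)
- 5 h 03 (neighbours 4 h and 6 h)

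If one of these is lost, or the 4 h value is BLQ and therefore embedded, the rule either removes a bolus peak or joins one peak to the next. The subject's other period, with complete samples, is computed on a different basis. The within-subject difference in AUC, and in CL derived from it, then partly reflects the lost sample. Those differences are where an effect of nortriptyline on morphine exposure would be looked for.

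**Working it through.** The protocol gives no morphine AUC to reproduce, so this is an illustration.

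**Inputs from the protocol.** Clearance is 21.1 ml/min/kg; 21.1 × 60/1000 = 1.266, which agrees with the stated 1.27 L/h/kg. Volume is 2.9 L/kg. Both are in section 2.2.2, morphine pharmacokinetics. Doses and sampling times are as above.

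**Assumptions.** 70 kg; one compartment; study morphine BLQ (set to 0) at pre-dose and 1 h; trapezoid from 0 h, either linear-up/log-down or all-linear.

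**Profile.** CL = 1.27 × 70 = 88.9 L/h; V = 2.9 × 70 = 203 L; k = 88.9/203 = 0.438 per h. Each dose contributes (dose/V)·exp(-k·time since dose). True AUC = 10,000 µg / 88.9 L/h = 112.5 ng·h/mL.

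| Time | 1 h | 2 h 03 | 4 h | 5 h 03 | 6 h | 8 h | 24 h |
|---|---|---|---|---|---|---|---|
| ng/mL | 0 | 14.46 | 6.16 | 37.62 | 24.82 | 10.34 | 0.01 |

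**Complete data, linear-up/log-down.** Segments from 1 h on: 7.59 + 18.96 + 22.98 + 29.24 + 33.07 + 23.58 = 135.4. All-linear gives 198.3.

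**One sample lost, linear-up/log-down:**

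- 2 h 03: the line from 1 h to 4 h has area (0 + 6.16)/2 × 3 = 9.23. It replaces 7.59 + 18.96 = 26.55. AUC falls to 118.1.
- 5 h 03: the line from 4 h to 6 h has area (6.16 + 24.82)/2 × 2 = 30.97. It replaces 22.98 + 29.24 = 52.22. AUC falls to 114.2.
- 4 h: the line from 2 h 03 to 5 h 03 has area (14.46 + 37.62)/2 × 3 = 78.12. It replaces 18.96 + 22.98 = 41.94. AUC rises to 171.6.

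| Lost sample | Log-down: AUC, change from 135.4 | Linear: AUC, change from 198.3 | CL change (log-down) |
|---|---|---|---|
| 2 h 03 | 118.1, -13% | 179.8, -9% | 135.4/118.1: +15% |
| 5 h 03 | 114.2, -16% | 176.6, -11% | 135.4/114.2: +19% |
| 4 h | 171.6, +27% | 233.3, +18% | 135.4/171.6: -21% |

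**Faster distribution (assumption).** With two compartments, central volume 1.0 down to 0.25 L/kg, inter-compartmental clearance 2 L/h/kg and total volume 2.9 L/kg, the log-down shifts are -22% to -29% (2 h 03), -36% to -51% (5 h 03) and +58% to +89% (4 h).

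**Integrating each bolus separately.** C0 is back-extrapolated to 2 h and 5 h, and the first-dose decline is extended to 5 h. In one compartment the 2–5 h window is 0.73 + 18.96 + 4.98 = 24.7. The window from 5 h to 24 h is 1.90 + 29.24 + 33.07 + 23.58 = 87.8. The total is 112.5, equal to the true value. In the two-compartment range the total is 129.8 to 181.5, which is +15% to +62%. That remainder is error from sparse sampling after each bolus.

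**The case against.** Much of the case on the other side stands.

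- **The zero rule is right.** No study morphine is given before 2 h, so setting a BLQ value at 1 h to 0 is correct.
- **The complete-data excess is not a stated error.** A plain trapezoid across the boluses would overstate AUC (+20% log-down, +76% linear in one compartment). A reader might infer that the protocol prescribes this. It does not: trapezoid type and morphine time zero are not stated, and processing is referred to an SOP that may insert dose times. Any such bias has the same form in both treatments and largely cancels within subject.
- **Losing a 3-minute sample does not worsen accuracy in the one-compartment case.** It moves the inflated 135.4 towards the true 112.5 (118.1 or 114.2). The harm is that the two periods stop being comparable. Losing the 4 h sample does move AUC away from the truth, to 171.6.
- **The stakes are limited.** PK is secondary and summarised descriptively, the only planned contrast is for pharmacodynamic endpoints, and the study is declared exploratory. Section 2.10.4 gives PK sampling precedence, so losses should be few. One affected subject among 24 similar ones moves a treatment mean by only about 0.7% (16%/24) to 1.1% (27%/24).

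The unseen SOP does not dispose of the point. Section 2.13.9 states its own rule without qualification. If the SOP bars interpolation across a dose, the two texts conflict and the protocol needs the exception.

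**Conclusion.** The point holds at moderate weight. A stated rule, followed exactly, interpolates across an IV bolus when any of three morphine samples is lost. That period's AUC then changes by -9% to -13% (2 h 03), -11% to -16% (5 h 03) or +18% to +27% (4 h), and CL moves the opposite way.

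The sizes rest on one compartment, 70 kg and a trapezoid from 0 h, and they grow if distribution is faster. The model is only illustrative: its half-life is 0.693/0.438 = 1.6 h, against the 15.1 h cited in section 2.2.2. The direction of each shift was the same in every case run.

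The documents do not support the stronger reading that the planned morphine AUC is wrong for every subject, because the protocol does not fix the integration method that would make it so.

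**What to change.** In section 2.13.9, limit the interpolation rule and add a morphine paragraph that says:

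- No interpolation or trapezoid crosses a morphine dose.
- Morphine AUC is integrated per dosing window: 2–5 h, and 5 h to the last measurable concentration.
- C0 is back-extrapolated to each bolus time. The value just before the second bolus is extrapolated log-linearly from 2 h 03 and 4 h.
- A window's AUC, and the total AUC and CL that depend on it, are reported as not calculable for that subject-period if its 3-minute sample is missing or BLQ. The same applies to the first window if the 4 h sample is missing or BLQ.
- The present rule stays for oral nortriptyline.

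Check that the SOP on non-compartmental analysis agrees. The cost is a few sentences and a small programming change. A few subject-periods may lose an AUC, and the sparse-sampling error after each bolus remains.

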# 2.13.10 Procedure for reporting any deviation(s) from the original statistical plan

Deviations from the original statistical plan will be documented in the clinical study report.

#### 2.14 ETHICAL CONSIDERATIONS

#### 2.14.1 Declaration of Helsinki

The investigator will ensure that this study is conducted in full compliance with the protocol, the principles of the Declaration of Helsinki (www.wma.net), ICH GCP guidelines (http://www.ich.org/products/guidelines.html), and with the laws and regulations of the country in which the clinical research is conducted.

### 2.14.2 Recruitment and informed consent procedures

It is the responsibility of the investigator to obtain written informed consent from each individual participating in this study after adequate information of the study. Potential subjects will reach out to CHDR when they are interested in participation. After a brief explanation as stated in the Subject Information Sheet, a meeting will be planned with the subject for the medical screening. Prior to screening, the potential subjects will receive the informed consent document via mail with detailed information on the study and contact details in case of questions. Before signing the ICF the potential subjects will watch an informational video on the trial. This includes the aims, methods, objectives and potential hazards of the study and an explanation that subjects are completely free to refuse to enter the study or to withdraw from it at any time for any reason. If subjects are interested in the study participation, they can sign the Informed Consent and their study participation can begin. Subjects always have the opportunity to discuss their study participation and questions with a CHDR physician before the information visit by phone or during the information visit, screening or clinical conduct with the CHDR physician. In accordance with regulations, sufficient time is given for subjects to understand what their participation means, but no minimum amount of time is specified or required. The Informed Consent and Subject Information will be provided in the local language/Dutch.

# 2.14.3 Benefits and risks assessment, group relatedness

Please refer to Subsection 3.

## 2.14.4 Compensation for injury

The investigator has an insurance that is in accordance with the legal requirements in the Netherlands (Article 7 WMO, under 1). This insurance provides cover for damage to research subjects through injury or death caused by the study. The insurance applies to the damage that becomes apparent during the study or within 4 years after the end of the study. The investigator has a liability insurance that is in accordance with article 7, under 9, of the WMO.

### 2.14.5 Compensation for subjects

The subjects will receive a monetary payment as compensation. This compensation is based on a national consensus to avoid financially enticing potential subjects in participating in clinical trials by an agreed standard amount per study characteristics; subject burden, time input, invasive measurements, measurements, restrictions, and duration of the trial. The compensation is a sum of all study characteristics The amount per study characteristic is according to the 'wage payment model'. This is based on the minimum wage, time investment, and burden. The compensation will therefore never be more than necessary as to serve as an enticement for participation.

### 2.14.6 Compensation for investigators

**TBD** 

## 2.14.7 Other ethical considerations

No other ethical considerations are applicable for this study.

## 2.15 ADMINISTRATIVE ASPECTS, MONITORING AND CONFIDENTIALITY

The investigator will ensure that this study is conducted in full compliance with the protocol, ICH Good Clinical Practice (GCP) guidelines (https://www.ich.org/page/ich-guidelines), and with the laws and regulations of the country in which the clinical research is conducted.

This study will be conducted according to applicable CHDR's SOPs. Quality assurance will be performed under the responsibility of CHDR's Quality Assurance manager.

## 2.15.1 Approval initial application and substantial modifications

The trial protocol, informed consent form, subject information leaflet, investigational medicinal product dossier, investigators brochure and any other documents required by the Regulation will be submitted for the regulatory approval before the clinical trial is started via CTIS.

The sponsor will also submit and obtain approval for substantial modifications to the original approved documents via CTIS.

A 'substantial modification' (SM) is defined in the CTR as any change to any aspect of the clinical trial which is made after notification of a decision referred to in Articles 8, 14, 19, 20 or 23 and which is likely to have a substantial impact on the safety or rights of the subjects or on the reliability and robustness of the data generated in the clinical trial.

Non-substantial modification (NSM)

Non substantial modifications (i.e., without substantial impact on the safety or rights of the subjects and/or the reliability and robustness of the data and when the information is not necessary for oversight) should not be notified as such. These changes should be implemented during the next substantial modification, whenever the scope of the non-substantial changes matches with the scope of the application under evaluation, meaning:

- a. Part I non-substantial changes can be included in an application with a Part I or Part I and II scope;
- b. Part II non-substantial changes can be included in an application with Part II or Part I and Part II scope.
- c. Both Part I & II changes can be included in an application with Part I (only non-SM Part I will be applicable), Part II (only non-SM Part II will be applicable) or Part I and Part II scope.

Non-substantial modifications will not result in a new version of the protocol. These will be listed in a log which contains the trial title and EU CT number and a table describing the non-substantial changes according to CHDR SOP APRAMEND. In case of more than one non-substantial change simultaneously, the changes are all listed in the same table (first column, second row of the table).

The following changes are by definition non-substantial in this study:

- Significant increase in duration of the overall time of the trial, provided that the following conditions are met (79):
  - o the exposure to treatment with the IMP is not extended;
  - o the definition of the end of the trial is unchanged; and
  - o scheduled subject study visits arrangements are unchanged;
- If there is a change in one or more of these conditions, it would be considered to be a substantial modification.
- In case of low interventional trials, additional diagnostic or medical monitoring procedure which is not requested by a MSC if it does not pose more than minimal additional risk or burden to the participants.

- Minor clarifications to the protocol.
- The addition/deletion of exploratory and/or tertiary endpoints as recorded in the TMF with no significant effect on the conduct of the trial.
- A minor increase in the duration (<10%) of the trial.
- A change in the number of trial participants per Member State if the absolute number of participants in the trial is identical or the decrease/increase is insignificant.
- A change in amount and timing of the samples (maximum of 2 samples without a > 10% increase in the amount of blood taken and not exceed 500 ml of blood in total).
- Changes in assay-type and / or institution where an assay will be performed, provided that validated assays will be used.
- Editorial changes to documents in the submission dossier including the participant information
  materials and the protocol. An editorial change is defined as a modification in the documents
  of typographical errors and other modifications that in no way alter the meaning or content of
  the document.
- Determination of additional parameters in already collected materials, which are in agreement with the study objectives and do not provide prognostic or genetic information;
- Other statistical analyses than described in the protocol.
- A change in clinical staff, when this concerns regular staff members of CHDR who comply with internal regulations for training and authorisation.
- A change in dosing schedule in an ascending dose trial, provided the expected exposure of the subjects does not exceed the preset values indicated in this protocol.

#### **Urgent safety measures**

Urgent safety measures might become necessary to preserve the safety of the subjects included in the study. The requirements for approval should in no way prevent any immediate action being taken by the investigators in the best interests of the subjects. Therefore, if deemed necessary, an investigator can implement an immediate change to the protocol for safety reasons. This means that, exceptionally, the implementation of urgent safety measures will occur before submission of the changes.

If urgent safety measures are required while any assessment is still ongoing, the sponsor should take the appropriate measure and notify the MSC. A SM can then be submitted once the ongoing SM is finalised.

